### 6.2

- Non-English speaking participants
- Illiterate or Low Literacy participants
- Participants with visual or hearing impairments
- Status Relationship: Individuals with a status relationship with the PI or other study team members (e.g., employees, students, family members)

This study will enroll Spanish-speaking participants. Ideally, the study team member conducting the consent/assent process and study procedures will be fluent in Spanish. If not, they will utilize a translator employed by the school district, school-approved personnel who are fluent in Spanish, or UW-Madison or UW Health interpreter services.

### 6.3

- Individuals who are receiving inpatient or outpatient services for mental illness, developmental disability, or alcohol and other drug abuse (AODA)
- Individuals who are protectively placed by a court in a treatment facility
- Veterans/Military Personnel
- Emancipated minors
- Anyone especially vulnerable to manipulation or inducements for participation as a result of their illness or socioeconomic condition

This study will not include any of the populations listed above.

## 7.0 Recruitment Methods

### 7.1 Recruitment Source:

## PROTOCOL TITLE: SAFE AND HEALTHY SCHOOLS

Participants will be recruited by nursing staff at Madison Metropolitan School District elementary schools.

### 7.2 Methods to Identify Potential Participants:

Potential participants may learn about the study from the school nurse, nurse's assistant, or whichever school-approved personnel are coordinating or administering COVID-19 testing. The school nursing staff may recommend at-school COVID-19 testing if staff or students become symptomatic while they are at school. Additionally, MMSD sends COVID-19 Student Screening emails to parents every weekday morning. If parents indicate that one or more of their children have symptoms, they are prompted to take a screening survey, then school nurses review the survey. Nurses may talk with parents on the phone and recommend that they bring their child(ren) to school for testing. If parents agree to at-school testing, the nursing staff may inform the parent of the study. Additionally, if a parent has a symptomatic child who attends a different MMSD school (e.g., a child who attends middle or high school), the nursing staff may also recommend at-school testing for them, as well. If parents agree to at-school testing for any of their children ages 4-19, the nursing staff may inform them about the study. The nursing staff will ask whether a potential participant is interested in talking with a study coordinator.

There will also be a sign at the schools near the location where COVID-19 testing is taking place. The sign will ask if people are symptomatic and getting tested, and if yes, they may be eligible to participate in a study. It instructs people to "call the study coordinator now" if they would like more information. When they call the number provided, the study coordinator would talk with the potential participant or parent on the phone or in person to provide more information about study details and eligibility. The study coordinator will also be wearing a UW badge, so if they are in close vicinity of the sign, participants may also walk up to them to ask about the study. Additionally, the study team may gently approach potential participants to see if they are interested in learning more about the study.

### 7.3 Where, When and How Participants will be Recruited:

If an MMSD student, teacher or staff member develops one or more symptoms consistent with COVID-19, either at home or at school, they may confer with the school nursing staff. The staff may recommend COVID-19 testing at the school. If a symptomatic individual (or their parent, in the case of children) agrees to a nasal

## PROTOCOL TITLE: SAFE AND HEALTHY SCHOOLS

swab PCR test at the school, then staff will inform them about the opportunity to participate in research. School-approved personnel will ask if they are interested in speaking with a study coordinator, and if yes, they will connect them with a study coordinator. The study coordinator will provide more information, and if the potential participants indicate that they are eligible and interested in participating, they will complete the consenting process. When possible, this initial information discussion and the consenting process will be conducted in person. If school personnel talk to parents on the phone, then the study coordinator may also talk with parents on the phone. This may be necessary in certain situations, such as when a parent intends to have someone who is not a legal guardian pick their child up from school, such as an older sibling or grandparent. When needed, the school personnel will connect the parent and the study coordinator over the phone for the initial discussion and consenting process. There will also be a sign near the location where the COVID-19 testing is taking place that will instruct people to call the study coordinator at the time of testing.

There are times when symptomatic adults and children may come to the school for testing without first talking with school personnel. In these cases, school personnel would not be available to introduce the study. School-approved personnel, such as Accelerated Clinical Laboratories staff collecting the BinaxNOW and nasal PCR swabs, may also introduce the study to adults. Additionally, people getting tested may see the sign and call the study coordinator to learn more about the study. Or, if study team members are in the close vicinity of the sign, wearing a UW badge, then participants may walk up to the study coordinator to ask them about the study.

With the presence of a sign near the testing location, the study team members may also gently approach potential participants. For example, the study team may ask whether they have questions about the sign or are interested in learning more about the study. The study team will be careful to be respectful, rather than intrusive, in their approach.

### 7.4 Recruitment Materials:

Flyers describing the study are available in both English and Spanish. Schools could use the flyer, at their discretion, to inform the school community about the study that is taking place. School-approved personnel, such as ACL staff, could also use the flyer to inform potential participants about the study at the time they are eligible.

A sign describing the study will be placed near the location where COVID-19 testing is taking place. It instructs people to call the study coordinator if they are experiencing symptoms and getting tested.

## PROTOCOL TITLE: SAFE AND HEALTHY SCHOOLS

If the study team does not have a supply of BinaxNOW tests, the Lollipop Only flyer and poster will be used for recruitment.

### 7.5 Compensation:

All participants will be offered a small prize, such as a sticker or small toy, for completing the lollipop swab. All participants who complete an at-school BinaxNOW test will also be given a BinaxNOW COVID-19 Ag Card Home Test kit, which includes two tests and instructions in both English and Spanish. These test kits cost approximately \$20 at local retailers. Participants with a negative at-school antigen test will need to use one of the two tests to complete study procedures. Remaining tests may be used at participants' discretion.

For participants who have a negative at-school BinaxNOW test and therefore complete the at-home BinaxNOW test, this study will provide subjects or their parent/legal guardian, in the case of children, with a \$10 gift card. The gift card will be given to adults after completing the at-home BinaxNOW test. It is possible for people to participate in this research study more than once—they may be eligible each time they get a BinaxNOW test and nasal PCR at school, if they have not had a positive COVID-19 test in the past 3 months. Therefore, participants will be re-consented and compensated each time they participate in the study. If participants do not complete the virtual/home visit, they will not receive a gift card.

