## 1.0 Study Summary

Study Title	Safe and Healthy Schools
Brief Summary	This study will target Madison Metropolitan School District school children ages 4-19 and staff who have not had a previous positive COVID-19 test within the past 3 months. It will enroll children and adults for 1-3 days to explore whether serial “at-home” BinaxNOW testing is feasible and non-inferior to “at school” single PCR testing for the evaluation of symptomatic individuals with a negative initial BinaxNOW. It will also explore whether lollipop swabs are more acceptable and perform as well as nasal swabs with PCR testing.
Number of study sites	1
Study Design	Community-based empirical research
Primary Objective	(1) Determine whether “at-home” BinaxNOW testing is feasible for families, (2) Evaluate whether serial “at-home” BinaxNOW testing is non-inferior to “at school” single PCR testing, (3) Compare the acceptability of lollipop swabs and nasal swabs, and (4) Compare the performance of lollipop swabs to nasal swabs with PCR-based testing.
Secondary Objective(s)	NA
Research Intervention(s)/ Investigational Agent(s)	NA
Drugs/devices used on study (including any IND/IDE #)	This study will evaluate the BinaxNOW COVID-19 Ag Card and the “lollipop” swab sample collection method
Study Population	Madison Metropolitan School District school children ages 4-19 and staff
Sample Size	400 with negative at-school BinaxNOW and 50 with positive at-school BinaxNOW. Total n=450.
Study Duration for individual participants	Up to 5 days
Study Specific Abbreviations/ Definitions	PCR: polymerase chain reaction EUA: emergency use authorization

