### 3.2 Hypotheses to be tested:

**Aim 1.1:** “At-home” BinaxNOW testing will be feasible for families.

**Aim 1.2:** Serial “at-home” BinaxNOW testing is non-inferior to “at school” single PCR testing.

**Aim 2.1:** Lollipop swabs are more acceptable to individuals than nasal swabs.

**Aim 2.2:** Lollipop swabs will perform as well as nasal swabs with PCR-based testing.

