## PROTOCOL TITLE: SAFE AND HEALTHY SCHOOLS

the client's backup routine. If files are accidentally backed up, they will be manually removed from the backup and deleted permanently from all locations except REDCap. Additionally, the SMPH VPN via the Palo Alto Global Protect client, configured and available for use on all DOP endpoints, will be enabled and connected by the end-user on data collection endpoints whenever study data is being accessed or transferred.

The study team will make every effort to enter data directly into REDCap in real time. The study team will use a wireless hotspot for reliable internet connectivity, rather than relying solely on the school's Wi-Fi connection, to minimize the need for this emergency data collection protocol.

After this basic information is collected, the study coordinator will begin testing. If the participant did not already receive an at-school BinaxNOW test, then the study coordinator will collect the nasal swab for and administer the BinaxNOW test. When study staff collect the nasal swab for the BinaxNOW test, they may encourage parents/legal guardians to comfort their child. Participants under the age of 18 will only receive nasal swabs when their parent or legal guardian is physically present. If a potential participant is unwilling to have the study team collect a nasal swab, they will not be enrolled in the study.

Next, the study coordinator will guide the participant through completing a "lollipop" swab at school. The lollipop swab is obtained by having the participant suck on a swab for 20 seconds in the same way that they would suck on a lollipop. The study coordinator will ask whether they prefer the PCR nasal swab or lollipop collection method. The study coordinator will provide the lollipop swab to Exact Sciences or ACL for analysis. For Exact Sciences, it will be labeled with the study ID and date of collection. For ACL, lollipop samples will have a label and accompanying requisition form that will both contain the subject's full name, date of birth, and the date and time of collection.

If the study team does not have any BinaxNOW tests due to a supply shortage, study participation will end after the lollipop swab is collected. If BinaxNOW tests are available and the participant intends to do the at-home antigen testing, then the at-school antigen testing is required.

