## PROTOCOL TITLE: SAFE AND HEALTHY SCHOOLS

If the second test is not used during the study, the participant may keep it and use it in the future if they feel confident doing so. If a participant says that they do *not* think that they could accurately do the test on their own, the study coordinator would advise them to seek assistance from a medical provider.

To accomplish the aims of this study, the study team will also need access to the results from the nasal swab antigen and PCR tests collected by the school. Parents will learn the results of the antigen test, and they will share the results with the study coordinator. If the samples are processed at Exact Sciences Laboratories, they will share the test results of the nasal swab and lollipop PCR tests with the study team via Exact Science's instance of HIPAA-secure Box. If the samples are processed by ACL, then the study team will share the results of the nasal swab and lollipop PCR tests with the study team via a UW-Madison Cybersecurity-approved data sharing tool.

- 13.4 A data collection form is uploaded in ARROW. Below is a list of data elements. Note that all data elements will be collected from participants who complete the at-home BinaxNOW test—those whose initial at-school BinaxNOW test was negative. The data elements related to at-home BinaxNOW testing will not be collected from participants whose initial at-school BinaxNOW test was positive, as they will not complete the at-home test virtual visit.
  - Administrative information
    - Dates and locations (i.e., virtual or in-person) of study activities
    - Times of data collection and study activities
    - Confirmation of consent and assent
  - Participant information collected verbally and recorded in REDCap
    - Participant's first and last name
    - Participant's parent or legal guardian (in the case of children)
    - Address
    - Phone Number
    - Email Address
    - Questions about participant's opinions on data collection methods
  - Biosample Collection Date/Time
    - At-school BinaxNOW (collected by school or study team)
    - Nasal swab for PCR testing (collected by school)
    - Lollipop swab
    - BinaxNOW test (administered by participant/family)
  - Biosample Results

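### The small prize is attached to the lollipop swab alone, and nothing fixes whether the preference question is asked before or after it, so the acceptability comparison carries an avoidable risk of bias of unknown size

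*Combined protocol and SAP*

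**What the plan says.** Acceptability is part of the Primary Objective in section 1.0 ("3) Compare the acceptability of lollipop swabs and nasal swabs"). Section 3.2 gives Aim 2.1 a direction: "Lollipop swabs are more acceptable to individuals than nasal swabs".

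Three rewards appear in section 7.5:

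- For the lollipop swab: "All participants will be offered a small prize, such as a sticker or small toy, for completing the lollipop swab".
- For the at-school antigen test: "All participants who complete an at-school BinaxNOW test will also be given a BinaxNOW COVID-19 Ag Card Home Test kit". The kit is valued at about $20.
- For the at-home antigen test, a $10 gift card: "The gift card will be given to adults after completing the at-home BinaxNOW test".

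None of these is for the nasal PCR swab. That swab is taken outside the study team: the list of data elements in 13.4 has "Nasal swab for PCR testing (collected by school", and section 7.3 mentions staff of the second laboratory as collectors.

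Section 13.3 sets out the steps at school. "Next, the study coordinator will guide the participant through completing a" lollipop swab, it says, and after describing the swab it continues: "The study coordinator will ask whether they prefer the PCR nasal swab or lollipop collection method". The prize is not mentioned in 13.3, and 7.5 does not say when it is offered or by whom. Section 20.4 plans no analysis of the preference answer.

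**The concern.** Aim 2.1 is a within-person comparison of two ways of taking a sample. A fair comparison needs the options to differ only in the sampling itself. Here one option carries a toy or sticker from the study and the other does not. The person who guided the rewarded option asks the question, and the study hypothesis favours that option.

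If the prize is given or mentioned before the answer is recorded, some respondents may be rating the visit that came with a toy. A 4-year-old is more likely to do so than a teacher. Every participant is offered the prize, so there is no unrewarded group from which to estimate the effect and subtract it. A larger sample would narrow the interval around a shifted proportion without moving it back. At stake is whether the reported preference for the lollipop can be read as a preference for the swab.

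**Working it through.** **The plan's own figure.** The only analysis with a sample size is the NPV test in 20.2 (null 91%, alternative 95%, one-sided 0.05, 90% power, N=358). An exact one-sample binomial test reproduces it. The smallest n with at least 90% power is 358, with rejection at 335 or more true negatives, actual size 0.0487 and power 0.909. The normal approximation gives 352. This confirms the stated N but has no bearing on acceptability, for which the plan gives no sample size, power or test.

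**The two options side by side.**

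| | Lollipop swab | Nasal PCR swab |
|---|---|---|
| Who obtains it | Study coordinator (13.3) | School or its laboratory staff (7.3, 13.4) |
| Study reward stated | Sticker or small toy (7.5) | None |
| Position of the preference question | Next step described, same coordinator (13.3) | Not tied to this swab |
| Favoured by Aim 2.1 | Yes | No |

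The order of swab and question is in the text. The order of prize and question is not. The plan describes no matched reward, no self-completed answer, no separate interviewer and no rule that the answer comes before the prize.

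**Illustration of sensitivity.** The documents give no size for the bias, so every input here except the counts is an assumption: true preference 50:50, one independent two-way answer per person, an exact one-sided binomial test at 0.025, and a common shift s in the probability of naming the lollipop.

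- Critical count c: the smallest c with P(X ≥ c | n, 0.5) ≤ 0.025.
- False conclusion rate: P(X ≥ c | n, 0.5 + s).

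For n=450 (400+50, total enrolment), c=247. For n=358 (the Aim 1 completers), c=199.

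| Assumed shift s | n=450 | n=358 |
|---|---|---|
| 0 | 2.1% | 2.0% |
| 3 points | 22.5% | 17.7% |
| 5 points | 53.8% | 43.3% |
| 8 points | 91.7% | 83.6% |

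The 5-point row can be checked by eye: 450 × 0.55 = 247.5 expected lollipop answers, just above the critical 247, so about half of trials reject. The rate is higher at the larger n, which shows that more participants do not cure a shift.

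The shift s is an average over all respondents. If only a fraction f is sensitive to the prize, with shift d among them, then s = f × d. The plan gives no expected split between children and staff, so f is unknown.

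**The case against.** The strongest reply is that the plan may already do the right thing. Section 7.5 is silent on timing and 13.3 does not mention the prize, so the coordinator may well record the answer first. The data collection form and scripts are held elsewhere, and 13.4 lists opinion questions in the plural, so the number of items, the answer options and whether parent or child answers cannot be seen. This stands: a reader might infer that the prize is handed over and the question then put, but the text does not say so. What remains is that nothing prevents that order, and that the prize is tied by its wording to one option whenever it is given.

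Second, the kit of about $20 rewards a test that is also a nasal swab and could pull the other way. This stands in part. The question names the PCR nasal swab, and a test kit is unlikely to appeal to a young child as a toy does. Lollipop Only participants with no at-school BinaxNOW get the prize and no kit. The direction is therefore probable, not certain.

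Third, participants are aged 4 to 19 plus staff with no stated split, so it cannot be said that most respondents are young children. A sticker should matter little to adults and older teenagers. This stands, and it limits the average shift.

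Fourth, the error rates rest on assumptions throughout. No test of preference is planned that could be inflated, and section 7.5 allows people to take part more than once, so answers need not be independent. This stands; the rates show sensitivity only. If the true preference for the lollipop is strong, the conclusion could survive, though the reported proportion might still be too high.

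**Conclusion.** The point holds as a design weakness: a reward is tied to one of two compared options, and the order of prize and preference question is unspecified, for an objective listed as primary. It is a risk of bias of unknown size, probably toward the lollipop and greatest in young children, and possibly offset in part by the kit. The primary diagnostic outcome, NPV, is not affected.

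Two stronger readings go too far. One is that the trial has a false-positive rate of 23%, 54% or 92%. Those figures require a shift, a 50:50 truth, a test and 450 independent answers, and the documents supply none of these. The other is that analysis can do nothing. It cannot remove the bias, but preference in adults and by child age would show whether the result is concentrated in those most likely to respond to a prize.

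**What to change.** - Amend 7.5 so that the prize is for completing the school visit and not for the lollipop swab.
- Amend 13.3 so that the preference answer is recorded before the prize is offered.
- Add to 20.4 that preference is reported separately for adults and by child age.

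Prize, question and staff stay the same. The cost is a minor amendment and a script change. The revision that added compensation is marked in the revision history as a consent change, so the consent wording may need review too. Enrolment is due to finish in August 2022, so answers already collected under the present wording should be flagged and shown separately.

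Protection will be incomplete. Repeat participants will already know of the prize. For Lollipop Only participants the lollipop swab is the only study test at the visit, so the new condition for the prize is nearly the same as the present one, and the benefit there comes mainly from asking the question first.

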## 8.0 Consent/Accent Process

- 8.1 A trained study team member will obtain informed consent from all adult participants and all parent/legal guardians of child participants. The trained study team member will also obtain assent from all children. If a parent or legal guardian chooses to enroll more than one child in the study, the consent and assent process will be completed for each child enrolled. Children ages 4-14 will be assented using the Assent Script. Children ages 15-17 will be assented using the Consent Script. There will be minor differences in assent discussions depending on children's ages, as study team members will use age-appropriate language.

If the study team does not have a supply of BinaxNOW tests, or if a potential participant is unwilling or unable to complete at-home BinaxNOW testing, the Lollipop Only consent and assent will be used.

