### 20.2 Sample Size Justification:

For Aim 1, it is anticipated that the majority of initial BinaxNOW tests will be negative. It is hypothesized that the proposed two-day serial testing procedure using BinaxNOW tests in participants with an initial negative test will identify true negatives in >95% of participants. The primary diagnostic outcome measure will be the negative predictive value (NPV). The NPV of BinaxNow is ~91% in symptomatic subjects. For the proposed study, the NPV after the second test (24 hours after the first negative results), is assumed to be substantially higher than 91% since the first test was already negative. In order to detect a true NPV after the second test of at least 95% with 90% power at the one-sided 0.05 significance level, a sample size of N=358 participants with an initial negative test is required. To reach a sample size of N=358 participants with an initial negative test, BinaxNOW kits will be administrated to 400 participants. We intend to continue enrolling until we reach the target sample size of N=358 completing the at-home BinaxNOW test.

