## PROTOCOL TITLE: SAFE AND HEALTHY SCHOOLS

testing as gold standard), and reported along with the corresponding two-sided 95% confidence intervals. Formal non-inferiority testing of the lollipop swab test with PCR will be conducted with respect to sensitivity and specificity with a non-inferiority margin of  $\delta=5\%$  and a sensitivity/specificity of PCR of 99%. Statistical analyses will be conducted using SAS software (SAS Institute, Cary NC), version 9.4 or greater.

20.6 Handling of Missing Data: The primary analysis for evaluating the diagnostic utility of the BinaxNOW testing procedure will be based on the complete case principle. Since the analyses of this study won't involve any formal multivariate or longitudinal statistical modeling, no imputation-based analyses will be conducted.

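### Siblings and repeat enrolments can contribute correlated records, but the sample size, intervals, tests and kappa bootstrap make no allowance for this

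*Combined protocol and SAP*

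**What the plan says.** **Enrolment.** Section 7.5 states: "It is possible for people to participate in this research study more than once". Participants are re-consented and compensated each time. The stated limit is "if they have not had a positive COVID-19 test in the past 3 months", and no cap on the number of enrolments is given. Section 8.1 covers the case "If a parent or legal guardian chooses to enroll more than one child in the study", with separate consent and assent for each child. Section 7.2 makes sibling enrolment likely: "If parents agree to at-school testing for any of their children ages 4-19", nursing staff may mention the study, including for a symptomatic child who attends a different school in the district.

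**Analysis sets.** Sections 5.2, 5.3 and 20.3 include everyone with the required results. No rule limits a person to a first episode or a household to one record.

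**Sample size and methods.** Section 20.2 sets 358 completers, "with 90% power at the one-sided 0.05 significance level", to separate an NPV of 95% from 91%. It enrols 400 to reach that number and mentions no allowance for correlation. Section 20.4 gives two-sided 95% intervals without naming the method for proportions, non-inferiority tests on sensitivity and specificity, and a nonparametric bootstrap for kappa without naming what is resampled. Section 20.6, on missing data, says the analyses will not involve "any formal multivariate or longitudinal statistical modeling".

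**The concern.** Siblings tested at about the same time share exposure and often the same adult taking the swab. A repeat enrolment shares the person. Where such records are positively correlated, 358 records carry less information than 358 unrelated people.

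Two things are at stake. Confidence intervals computed as if records were independent would be too narrow, for NPV, PPV, sensitivity and specificity in both aims and for kappa in Aim 2. The one-sided NPV test could also reject a true null more often than 5% of the time. Sections 4.2, 4.3 and 20.2 count participants without saying whether someone who enrols twice counts once or twice, so even the target is ambiguous.

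**Working it through.** **Inputs from section 20.2.** Null NPV 0.91 ("The NPV of BinaxNow is ~91% in symptomatic subjects"), alternative 0.95, one-sided 0.05, power 90%, N = 358. Section 20.1 words the null as an NPV of at least 91%, which does not oppose the alternative; I read it as at most 91%. I take all 358 as the NPV denominator, as the plan does. The true denominator is those whose second test is negative, so slightly fewer.

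**Step 1: reproduce 358.** Let X be the number of true negatives. Under independence X is binomial, and the smallest cut-off that holds the level is 335:
- P(X ≥ 335 | 358, 0.91) = 0.0487
- P(X ≥ 334 | 358, 0.91) = 0.0726, which is too large
- P(X ≥ 335 | 358, 0.95) = 0.909

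No smaller N reaches 90% power with the level at or below 0.05; N = 345, for instance, reaches 0.8992. The usual normal approximation gives 352. Both calculations assume independent records.

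**Step 2: add clustering.** With intra-cluster correlation ρ,

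design effect = 1 + ρ × [share in pairs × (2 − 1) + share in trios × (3 − 1)]

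Effective N is 358 / design effect, and a correct interval is wider by √(design effect). For example, 20% in pairs at ρ = 0.3 gives 1 + 0.3 × 0.20 = 1.06, effective N 358 / 1.06 = 338 and a width factor √1.06 = 1.030. For 40% in pairs and 20% in trios at ρ = 0.5: 1 + 0.5 × (0.40 + 0.20 × 2) = 1.40.

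**Step 3: level and power of the same rule (reject at 335 or more of 358).** Each cluster is beta-binomial with correlation ρ, and the exact distribution of the total comes from convolution, using whole clusters (18 pairs for 10%, 36 pairs for 20%, and so on). The shares and ρ are assumptions.

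| Records in clusters | ρ | Design effect | Effective N | Level | Power | Width factor |
|---|---|---|---|---|---|---|
| none | – | 1.00 | 358 | 0.0487 | 0.909 | 1.000 |
| 10% in pairs | 0.1 | 1.01 | 354 | 0.0495 | 0.908 | 1.005 |
| 20% in pairs | 0.1 | 1.02 | 351 | 0.0503 | 0.907 | 1.010 |
| 20% in pairs | 0.3 | 1.06 | 338 | 0.0536 | 0.902 | 1.030 |
| 30% in pairs, 10% in trios | 0.3 | 1.15 | 311 | 0.061 | 0.894 | 1.07 |
| 40% in pairs, 20% in trios | 0.5 | 1.40 | 256 | 0.081 | 0.872 | 1.18 |

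**Step 4: repeat visits separately.** A false negative here means a positive nasal PCR, and a positive test bars re-entry for 3 months. A simulation in which 30% of people attempt a second visit at ρ = 0.3 gave a design effect of 1.02 and a level of 0.050 when a first-visit false negative blocks the second visit. Without that block it gave 1.15 and 0.060. The blocked case describes repeats within 3 months; a return after that interval would behave more like the unblocked case.

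**The case against.** **Independence is never stated.** A reader might infer that the plan declares all records independent. It does not. That reading rests on silence about the unit of analysis and on the match between 358 and a binomial calculation. The sentence in section 20.6 explains why no imputation will be done; it neither asserts independence nor rules out clustered intervals. This stands. The point is the missing allowance, not a stated false assumption.

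**The level need not be exceeded.** A reader might also infer that the test certainly exceeds 5%. Because the exact rule starts at 0.0487, light clustering leaves it below 0.05, and modest clustering moves it by tenths of a percentage point. This stands too.

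**Repeat enrolment is the weaker source.** The 3-month bar removes most repeat false negatives, as step 4 shows. This stands for NPV and leaves siblings as the main source.

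**A high sibling correlation is doubtful.** Each child must be symptomatic, the NPV denominator drops any child with a positive antigen test, and a coordinator observes the home test and verifies the result (sections 13.3 and 16.1). This argues against the extreme row of the table but does not show that the correlation is zero.

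**Swab preference.** It is tempting to say that standard errors for preference are understated as well. Section 20 specifies no interval or test for preference, so the documents do not support that.

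**Conclusion.** The concern holds in a limited form. The enrolment rules admit siblings and repeat episodes, every qualifying record enters the analysis, and neither the sample size nor the methods allow for correlation. If it is positive, the reported intervals will be somewhat too narrow and the NPV test can exceed its level.

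The likely size is small: with 10-20% of records in pairs and ρ of 0.1-0.3, intervals should be about 0.5-3% wider, the level is about 0.049-0.054 and power remains above 90%. It becomes material only with heavy clustering: a level of about 0.08 and power of about 87% need 60% of records clustered at ρ = 0.5. These ranges rest on assumed inputs. I quantified the NPV test only, and did not assess clustering by school. The gap should be closed because closing it is cheap and depends on information that will not be kept.

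**What to change.** 1. State in sections 4.2, 4.3 and 20.2 whether 358 counts people or episodes.
2. Define the unit of analysis in section 20.3 and keep a coded person identifier and a coded household identifier in the analysis file. Name, address and guardian are already collected (sections 13.3 and 13.4). The codes must be created before names and contact details are destroyed at study end and the data anonymised for banking (sections 19.2 and 19.4).
3. Compute the intervals and tests for NPV, PPV, sensitivity and specificity with household as the cluster, which also covers repeat visits by the same person. Standard cluster-robust or GEE intervals behave poorly for proportions near 100% or with few positives, so name a method suited to these, such as a Wilson or exact interval on the effective sample size.
4. Resample households, not records, in the kappa bootstrap.
5. Add a sensitivity analysis using each person's first enrolment, or one record per household.

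The cost is plan wording, two coded identifiers and slightly wider intervals. No new participants or procedures are needed.
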